#### Other Cardiovascular and Pulmonary Complications

Other cardiovascular and pulmonary complications are defined as a complication or any new diagnosis that is not related to the prosthesis, but is important to subsequent morbidity and mortality of the patient, e.g., cardiomyopathy, aortic aneurysm, chronic obstructive pulmonary disease, pulmonary embolism. These events may be characterized by the following factors: necessity for intervention, new or unduly prolonged hospitalization, or death. Minor events of no importance to the patient's valve related morbidity or mortality, such as acute upper respiratory infections, should not be reported.

#### Other Non-Cardiovascular Complications

Neurological, gastrointestinal, hepatic, renal, and other complications are defined as a complication or any new diagnosis that is not related to the prosthesis but is important to subsequent morbidity and mortality of the patient, e.g., cerebrovascular accident,

transient ischemic attack, ulcer bleeding, hepatic disease, coagulopathy, kidney failure, infection. These events may be characterized by the following factors: necessity for intervention, new or unduly prolonged hospitalization, or death. Minor events of no importance to the patient's valve related morbidity or mortality, such as acute intestinal virus infections, should not be reported.

#### 2.4.6 Echocardiography Procedures

In addition to preoperative echoes, echocardiographic evaluation of the study prosthesis **is required** when the patient is stable during the early postoperative follow-up (prior to discharge or 30 days, whichever occurs first); at 3-6 months and at the 1-year follow-up (between 11 and 14 months). Regurgitation and stenosis information is required for all remaining heart valves as these results may impact the study valve.

Preoperative echocardiography of the valves being replaced is required in this study. For preoperative echocardiographic data, the best available examination information will be used.

Record only one patient echocardiography examination per recording. Attach the following information to each recording:

- Patient study ID
- Name of the institution and investigator
- Date of the echocardiography examination

The echocardiography protocol used will generally follow that developed by FDA guidelines or ISO standards (Appendix A contains summary of the protocol), however, to provide a uniform method whereby data collection will be common to all echocardiography centers only one method will be used to derive the echo study output data. The derived data will conform to ISO standards. Additionally, only directly measured data will be provided by the center, and all calculated data will be derived centrally by the core lab. Regurgitation will be assessed by the investigator's echocardiographer and reassessed by the study cardiologist to provide for consistency across the centers.

Transthoracic echocardiographic examinations will follow a step-by-step progression of the following interrogation regions: left parasternal, apical and periapical, right parasternal, subcostal, and suprasternal. For each interrogation include 2D and M-mode recording for structure, function and timing data, and color Doppler for flow pattern to guide the pulsed (PW) and continuous (CW) Doppler measurements. It is understood that the right parasternal view is difficult to get in the immediate post-operative period. If needed, this view can be dropped from the early post-operative exam.

Specific Instructions for Completing CRF2

Provide the patient study ID and other basic information listed at the beginning of the form.

Using the echocardiography report from your center, provide the anatomical data collected from 2D or M-mode studies. Valve hemodynamics are to be gathered from the position giving the best signal. If the position used is different from those listed in the progressions noted in the previous section, then note the position used for either pressure or regurgitation measurement.

Provide the hemodynamic data requested on the form from the view that provides the best signal. Summarize the results of the echocardiography exam and forward the recording of the session to the monitor.

For the purposes of this study regurgitation will be graded as none, trivial, 1+= mild, 2+= moderate, 3+= moderately severe, or 4+= severe.

Subaortic diameter measurement should be made from the trailing edge of the left septal echo to the leading edge of the anterior mitral leaflet echo. If severe left ventricular hypertrophy or bowing of the anterior mitral leaflet exist, this measure should not be made and the space should be left blank on the CRF. If in pediatric patients this dimension cannot be reliably measured as judged by the core echocardiographer, the nominal valve tissue annulus diameter (i.e. 17mm for the aortic valve) will be used for aortic orifice area calculations and the orifice area calculation by continuity equation will be skipped for the mitral valve.

Diastolic filling period in this study is arbitrarily defined as the time from the onset of flow to when flow falls below 10 cm/sec. This allows calculation of transmitral flow.

#### 2.4.7 Blood Studies for Hemolysis

Preoperatively and at each scheduled late follow-up the study protocol calls for blood studies to determine the level of hemolysis in the patient. The specific tests required are red cell count, white cell count, hemoglobin, hematocrit, plasma free hemoglobin, serum lactate dehydrogenase (SLDH), reticulocyte count, and serum haptoglobin. When SLDH is elevated above the upper end of normal, it is to be fractioned and quantified by its five isoenzymes.

Blood tests must be processed according to local requirements. Local laboratory normal ranges for all tests must be provided.

#### 2.4.8 Explants

Whenever a valve reoperation occurs whether or not as a result of one of the complications described in Section 2.4.5 above complete and return CRF 6. Explants are requested at autopsy whenever practical. Reoperative explants may also occur. Return of explanted valves within the study is required.

Specific explant analysis requirements are included in this plan. An explanted mechanical valve prosthesis refers to a study valve that has been removed from the patient at reoperation or autopsy. The recommended procedures have been developed to ensure accuracy, consistency and completeness of the analysis of explanted valves. This section outlines in detail the procedures for explanting, recording data and returning the explanted valves.

Explanting the Valve

When explanting a valve at reoperation or autopsy:

- 1. Inspect the mechanical valve prosthesis prior to removal including the condition of the annulus for evidence of dysfunction such as thrombi, paravalvular leak, vegetations, pannus overgrowth. Culture of pertinent areas of the valve when appropriate is mandatory.
- 2. Examine the lining of the chambers of the heart, both proximal and distal to the valve for possible jet lesions or endocardial fibrosis.
- 3. Special attention should be paid to the possibility of extrinsic interference with the valve function, particularly by retained mitral valve leaflet tissue or sutures.
- 4. If possible, photograph the mechanical valve prosthesis *in situ*. For valves obtained at autopsy, photograph both the inflow and outflow aspects.
- 5. DO NOT rinse the valve.
- 6. Request an explant kit from the sponsor and place the valve in the jar provided in the explant kit.
- 7. If no explant kit is available, place the valve in either 1% glutaraldehyde solution or 10% buffered formalin until a kit is obtained.
- 8. Record observations on CRF6 in the appropriate locations.

Data and Shipping Requirements

To send the data and return the valve to study sponsor:

- 1) Attach a copy of the reoperative or autopsy report to the appropriate CRF6.
- 2) Attach any *in situ* photographs to CRF6.
- 3) Ship the valve as instructed in the explant kit, clearly marked as an explant, and inform the monitor by telephone or telefax of its shipment.
- 4) Notify your clinical research monitor if the valve cannot be returned.
- 5) If the valve is examined by a pathologist at the hospital where it was explanted, send that report to the monitor as well.

Each returned heart valve received by the sponsor (or monitor) will be tracked and analysis information compiled and stored. Each explant will be analyzed by the independent study pathologist and his/her report will be provided to the investigator and monitor.

### 2.4.9 Monitoring Procedures

The monitor of the study shall be a professional staff member of the Clinical Studies Department of the sponsor or a consulting Clinical Research Organization. Monitoring of the clinical trial will be a continuous process to ensure that high quality data are obtained through compliance with the investigational plan. Case report forms

or electronic data will be reviewed for accuracy, completeness, and conformity with requirements. Particular attention will be paid to blood damage studies, echocardiography and complication reporting. Frequent communication will be maintained with each clinical center to keep both the center and the sponsor informed and aware of the clinical trial progress.

On-site monitoring of all study centers will occur at least annually to ensure continued acceptability of the center by assessing compliance to the investigational plan, adherence to data collection procedures, verification of the accuracy of submitted clinical data to the patient's source documents, maintenance of clinical trial records, verification of informed consent, and verification of control of test articles. Reports of each center's visits will be provided to the investigator and sponsor, and if necessary, appropriate corrective action will be taken to ensure compliance to the investigation plan.

#### Preinvestigation Visit:

Preinvestigation visits will be conducted by the sponsor or sponsor representative to review the investigational plan and discuss the report of previous investigations with the investigator and staff to assure that they:

- Understand the investigation of the device and the requirements for its accountability.
- Understand the nature of the investigational plan including record, reports and recruitment of patients.
- Understand the requirement for an adequate, well controlled clinical trial.
- Understand and accept the obligation to conduct the clinical investigation in accordance with applicable national regulations.
- Understand and accept the obligation to obtain Ethics Committee or Institutional Review Board (IRB) review and approval before the clinical trial may be initiated, ensure continuing review of the trail by the Ethics Committee or IRB and keep the sponsor informed of any actions by the Ethics Committee or IRB that concern the clinical trial.
- Have access to an adequate number of suitable patients to conduct the investigation.
- Have adequate facilities and staffing to conduct the investigation.
- Have sufficient time from other obligations to fulfill the responsibilities of the investigation.
- Particular attention will be given complication reporting.

Annual Center Monitoring Visit:

Following the preinvestigation visit, on-site monitoring visits will be conducted at least annually.

On-site monitoring visits will assess the progress of the clinical trial and identify any concerns that result from device performance and review of the investigator's clinical trial records, study management documents and patient consent forms. This review includes adherence to the investigational plan, Ethics Committee or IRB review of the clinical trial and its progress and maintenance of records and reports.

To assure the integrity of the clinical trial data, individual patient records and other source documents are compared to reports from the investigator to determine that:

- The information recorded in the case report forms and/or reports is accurate, complete and legible.
- There are no omissions in the case report forms of specific data (e.g., development of an intercurrent illness)
- Missing follow-up visits are documented in the reports.
- Patients failing to complete the clinical trial and the reason for failure are noted in the reports.
- Informed consent has been documented.

A record of the monitor's findings will be maintained by the sponsor and investigator and will contain the following information:

- The date(s) of the visit.
- The name(s) of the monitor(s) who conducted the visit.
- The name(s) and address of the investigator(s) and other center staff who were visited.
- A statement of the findings, conclusions and any actions taken to correct deficiencies observed during the visit.

Resolution of concerns and completion of assigned tasks will be documented by the monitor.

#### 2.4.10 Statistical Analyses

Descriptive statistics will be calculated for all hemodynamic or hemolytic measures taken in the trial. These will be compared by t-test or chi square test as appropriate to PMA results at equivalent time periods. Demographic data will also be summarized using descriptive statistics and compared to PMA data where practical. Limited sample size may limit the power of these comparisons. Adverse event data will be evaluated both early and late in accordance with the AATS/STS guidelines on reporting valve studies. Again, limited sample size may make comparisons to PMA data inappropriate and may make rate calculations unreliable. However, calculations will be done and comparisons will be made to the PMA data; and an assessment of the power of these comparisons will be made.

Screen failures will also be examined for potential biasing effects on the trial. Analysis will be dictated by the information available, if any.

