#### 1.0 PURPOSE

The purpose of the proposed study is to assess the safety and efficacy of the 17mm On-X Aortic Prosthetic Heart Valve when used to replace diseased aortic valves and the 23mm On-X Mitral Prosthetic Heart Valve when used to replace diseased mitral valves in human subjects.

The On-X 17mm aortic valve will be implanted in approximately 20 and at least 15 patients and will be followed for 1 year. Enrollment of On-X 23mm mitral valve patients has been discontinued due to low enrollment potential. Follow-up of enrolled patients will continue according to the protocol for 1 year.

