#### Valve safety:

- Although sample size will limit the value of event rate calculations, early (30-day) and late time-related incidence and associated rate of all deaths and each valve related cardiovascular complication will be determined. Adverse events are those defined by the STS/AATS definitions, as well as all other cardiovascular complications. Rates of valve thrombosis, thromboembolism, hemorrhage (both all and major), endocarditis, hemolysis, hemolytic anemia, mortality, reoperation, valve explantation and prosthetic valve dysfunction (structural, non-structural and paravalvular leak (both all and major)) are primary safety endpoints to be evaluated using both linearized and actuarial statistical methods.
- Hemolytic potential of the valve will be measured using a CBC, reticulocyte count, serum haptoglobin, serum lactate dehydrogenase and plasma free hemoglobin.

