#### 2.1 STUDY DESIGN (SAMPLE SIZE)

Patients meeting all the appropriate criteria will be recruited for clinical trial participation. Enrollment is non-randomized, and continues until the sample size requirement is met, unless the sponsor terminates the clinical trial early for unforeseen reasons.

Submission for premarket approval in the U.S. will occur after international standards criterion of at least 15 patients will be followed for one year. This follow-up will include echocardiography, blood damage, NYHA status and any adverse events.

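### With 15–20 patients, chi-square is a poor choice for sparse categorical hemodynamic and hemolytic comparisons with the PMA; an exact or mid-p test should be named instead

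*Combined protocol and SAP*

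**What the plan says.** Section 2.4.10 opens with "Descriptive statistics will be calculated for all hemodynamic or hemolytic measures taken in the trial" and continues "These will be compared by t-test or chi square test as appropriate to PMA results at equivalent time periods". Read together, the two named tests apply to hemodynamic and hemolytic measures. The qualifier chooses between those two tests and offers no third. No exact test, continuity correction, minimum expected count or alpha is stated in the documents.

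Two categorical measures fall within that scope: hemolysis, defined from laboratory criteria in Section 2.4.5, and regurgitation, graded in Section 2.4.6 and on CRF 2.

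The sample is small by design. Section 1.0: "The On-X 17mm aortic valve will be implanted in approximately 20 and at least 15 patients and will be followed for 1 year". Section 2.1 ties this to the "international standards criterion of at least 15 patients will be followed for one year".

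Adverse events are handled separately. The valve safety paragraph of Section 2.0 has them "to be evaluated using both linearized and actuarial statistical methods". Section 2.4.10 warns that "limited sample size may make comparisons to PMA data inappropriate and may make rate calculations unreliable" but then commits: "calculations will be done and comparisons will be made to the PMA data". It names no test for that comparison.

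**The concern.** The chi-square p-value is a large-sample approximation. When one group has 15 to 20 patients, any uncommon category has a very small expected count and the approximation can be poor. For rare outcomes the usual result is a p-value that is too small when one or two events fall in the small group.

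The measures affected are central to the trial's purpose. Section 4.0 attributes the absence of this size in the US to missing hemodynamic and blood damage data, and Section 2.1 links the trial to a premarket submission. An apparent difference in hemolysis or regurgitation from the PMA valves could rest on one patient and on the choice of test.

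**Working it through.** **Inputs from the documents.** n = 15 (minimum) or 20 (approximate plan), Section 1.0. Tests: t-test or chi-square, Section 2.4.10. The figure of 15 comes from an external standard. With no alpha, power, effect or rate given, there is no sample-size calculation to reproduce.

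**Assumptions.** PMA size N = 100, 200 or 400; true rates 0.5% to 10%, equal in both groups; two-sided alpha 0.05; Pearson chi-square without continuity correction unless stated.

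**Step 1: expected counts (no PMA figure needed).** Expected 17 mm count = n × pooled rate.
- Below 5 when the rate is under 5/15 = 33% or 5/20 = 25%.
- Below 1 when the rate is under 1/15 = 6.7% or 1/20 = 5%.
- Regurgitation has six grades in Section 2.4.6 and five amounts on CRF 2. The average expected count per grade is 15/6 = 2.5 to 15/5 = 3 with 15 patients, and 20/6 = 3.3 to 20/5 = 4 with 20. Not every cell can reach 5.

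**Step 2: one event in the 17 mm group.** For a/n against b/N, with T = n + N and m = a + b:

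X² = T[a(N − b) − b(n − a)]² / [n N m (T − m)]

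- 1/15 vs 0/100: X² = 115 × 100² / (15 × 100 × 1 × 114) = 6.73, p = 0.0095. Fisher: 15/115 = 0.130.
- 1/15 vs 1/200: X² = 215 × 185² / (15 × 200 × 2 × 213) = 5.76, p = 0.016. Fisher: 1 − (200 × 199)/(215 × 214) = 0.135.
- 1/15 vs 1/100: X² = 115 × 85² / (15 × 100 × 2 × 113) = 2.45, p = 0.12. Fisher: 0.245.

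The same calculation for other tables:

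| Table | Chi-square p | Fisher p |
|---|---|---|
| 1/15 vs 4/400 | 0.048 | 0.169 |
| 1/20 vs 2/400 | 0.020 | 0.136 |
| 1/15 vs 2/200 | 0.071 | 0.196 |
| 1/20 vs 2/200 | 0.141 | 0.250 |
| 1/15 vs 8/400 | 0.223 | 0.284 |

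With no control events, one study event reaches p < 0.05 only from N = 57 (n = 15) or N = 77 (n = 20). Against a fixed control rate it does so only below about 1.2% (n = 15) or 0.9% (n = 20).

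**Step 3: type I error.** Sum the product of two binomial probabilities over all tables with p < 0.05. Ranges are over n = 15, 20 and N = 100, 200, 400.

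| True rate | Uncorrected chi-square |
|---|---|
| 0.5% | 4.5–7.1% |
| 1% | 5.6–9.2% |
| 2% | 5.2–6.5% |
| 3% | 4.9–5.5% |
| 5% | 3.7–4.7% |
| 10% | 3.7–4.1% |

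At 1%, the values for N = 100, 200, 400 are 5.7%, 6.2%, 9.2% (n = 15) and 7.3%, 8.3%, 5.6% (n = 20).

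**Step 4: alternatives on the same grid.** Ordinary Fisher: 0.2–2.7%. Mid-p (the Fisher p-value less half the probability of the observed table): at most 4.5% at rates of 0.5, 1, 2, 5 and 10%, and 4.6% if 3% is included. Yates-corrected chi-square: at most 2.0%.

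**Step 5: what the alternatives leave.** With no control events, Fisher p = n/(n + N), so 1/15 vs 0/300 gives 15/315 = 0.048. Mid-p halves this: 1/15 vs 0/200 gives 15/(2 × 215) = 0.035, against 0.065 for 1/15 vs 0/100.

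**The case against.** The strongest reply has five parts.

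- **No decision depends on these p-values.** The plan sets no alpha, hypothesis or pass/fail rule, and it warns that small numbers limit the comparisons. That lowers the stakes. But the warning concerns low power and unreliable rates, which is a different fault from a test that rejects too often, and the comparisons go ahead regardless.
- **The inflation is modest and local.** This stands. The 9.2% is one cell (n = 15, N = 400, rate 1%), and the same cell at 0.5% is 6.9%. A reader might infer that error is nearly doubled for rare outcomes generally; the calculations do not show that.
- **It depends on the uncorrected test.** This stands. The plan does not say which form is meant. With Yates' correction, 1/15 vs 0/100 gives p = 0.27 and 1/15 vs 1/200 gives p = 0.31.
- **Most measures in scope are continuous.** Gradients, orifice areas, cardiac output and individual blood tests would go to the t-test. No rate is given for hemolysis or regurgitation, so neither is shown to be rare. This stands, though the regurgitation cell counts in Step 1 are small whatever the rates.
- **Adverse events are outside the sentence.** A reader might infer that deaths, thromboembolism and the other safety endpoints will also be tested by chi-square. The text does not say so: it gives them linearized and actuarial methods and names no comparison test.

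**Conclusion.** The point holds in limited form. For categorical hemodynamic and hemolytic comparisons, the plan names only a test whose approximation is doubtful at n = 15–20. Under the stated assumptions its type I error ranges from 3.7% to 9.2%: above nominal in most cells at rates of 0.5–2%, close to 5% at 3%, and slightly below it at 5–10%.

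It would be too strong to say that an expected count below 1 is enough for a single event to be significant. That also needs the uncorrected test, a control rate of about 1% or less and enough controls. PMA size, outcome rates, alpha and the form of chi-square are all assumed, so the size of the problem can only be ranged. This is a cheap improvement and does not threaten the trial's validity.

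**What to change.** In Section 2.4.10, for categorical hemodynamic and hemolytic comparisons with the PMA, replace the chi-square test with an exact test, preferably the mid-p version, and report an exact confidence interval for the difference in proportions. State the alpha and sidedness. For regurgitation, state in advance whether the full grade table or a fixed cut-point is compared.

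For adverse events, say which comparison method applies. The same exact method can be adopted there for event proportions, as an addition to the plan.

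The cost is wording only: no patients, visits or data. The drawback is conservatism and some loss of power, greater with ordinary Fisher than with mid-p. Neither removes every single-event result (Step 5), so counts and the interval should be shown beside any p-value. A mid-p test and an exact interval can disagree at the margin, so the plan should say which one leads.

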#### Form/Data

Preoperative Form CRF 1
Echocardiography CRF 2
Echo Recordings
Blood Sample to Lab
Implantation Data Card
Operative Form CRF 3
Early Follow-up CRF 4
Late Follow-up CRF 4
Complication CRF 5
Reoperative CRF 6
Death Summary/ Autopsy
Explant Summary

Х				
Х		Х	Х	Х
X		Х	Х	Х
0			Х	Х
	Χ			
	Χ			
		Х		
			Х	Х
	0	0	0	0
	0	0	0	0
	0	0	0	0
	0	0	0	0

Χ	Required	Data
0	Required	only if needed
	Not	applicable

All appropriate sections of the CRFs must be filled out accurately and completely. Echocardiography recordings are to be forwarded to the sponsor for eventual assessment by a core cardiologist. All case report forms must be reviewed, signed and dated by the investigator(s). The CRFs should be sent expeditiously to the sponsor, when completed, and be kept in the patient record notebooks. Blood samples for hemolysis assessment are to be properly forwarded to the laboratory, per its protocol.

To protect patient confidentiality, the sponsor will use the information from the CRF's for statistical and device tracking purposes only and will treat medical records as confidential. For this reason, the sponsor is not routinely collecting patient names, but using patient initials for patient identification; thus better protecting patient confidentiality. A representative of the U.S. Food & Drug Administration or other appropriate regulatory authority may look at, and perhaps copy, some of the medical records; these organizations also have rules for protection of patient privacy that they must follow.

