#### 2.4.1. Preoperative Procedures

The investigator will determine and document on CRFs whether each patient meets the selection criteria previously outlined before enrollment into the study. He will also obtain informed consent for study participation from each patient prior to enrollment. A copy of the informed consent form will be kept by the investigator in the patient's study notebook. Patients not meeting the selection criteria or not receiving informed consent **should not** be enrolled in the study.

The investigator will determine and record on CRF1 each patient's demographics and relevant medical history, i.e., New York Heart Association (NYHA) functional class, cardiac rhythm, preoperative conditions, and diagnosis for valve replacement, etc. A preoperative echo/Doppler evaluation of the valve(s) being replaced is required according to the procedures of this study; a cardiac catheterization is not requested.

Blood studies on each patient will include: white blood cell count, red blood cell count, hemoglobin, hematocrit, serum lactate dehydrogenase (with fractionation by isoenzymes if above normal), plasma free hemoglobin, reticulocyte count, and haptoglobin. This will be recorded preoperatively, if possible, and at both follow-up intervals. The laboratory report including normal ranges will suffice as a CRF for these tests.

Specific Instructions for Form CRF1

These instructions are made to assist the study coordinator in filling out the form. Complete all items on the form. If information is unavailable to answer any item, make a note on the form. When asked to specify a particular answer, use a short description. On all check off lists, the space to be checked is either in front of, or below the answer. Please check any and all items that apply to the patient.

For patient study ID use patient initials. NYHA functional class uses the generally familiar nomenclature of that association. For the purposes of this study the commonly used classes of IIa and IIb are not used, either subgroup is considered class II. For infants and toddlers the Ross Scale functional classification can be substituted for NYHA classification anytime this data element is requested.

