#### 2.4.4 Late Follow-up Reporting

Late follow-up is required in the 3-6 month postoperative interval, and at 1-year (between 11 and 14 months postoperatively). Follow-up must be in person; telephone or questionnaire follow-up is unacceptable. A late follow-up form (CRF4) is due at each follow-up on each patient whether or not follow-up has occurred.

Late follow-up information includes in all cases the patient ID, cardiac rhythm (from electrocardiogram or echocardiogram), NYHA classification, and anticoagulant therapy information, including INR. Blood samples shall be drawn and forwarded to the local laboratory at each regularly scheduled late follow-up. These samples are the same as the preoperative tests and are handled in the same manner. Echocardiography studies are required at the 3-6 month and 1-year follow-up. Those data should be included at that time, but should also be added when done optionally at any other follow-up. For any new complication, a complication report (CRF5) must be completed and attached. All complications that have occurred between follow-up examinations must be reported on the appropriate form.

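### Section 2.4.10 compares hemolysis measures with the PMA unadjusted and plans no baseline-adjusted or within-patient analysis, although the same panel is called for before surgery (if possible) and at both late visits

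*Combined protocol and SAP*

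**What the plan says.** The safety objectives in section 2.0 include blood damage: "Hemolytic potential of the valve will be measured using a CBC, reticulocyte count, serum haptoglobin, serum lactate dehydrogenase and plasma free hemoglobin". Section 2.4.7 sets the timing: "Preoperatively and at each scheduled late follow-up the study protocol calls for blood studies to determine the level of hemolysis in the patient". Section 2.4.4 says of the late draws: "These samples are the same as the preoperative tests and are handled in the same manner".

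The preoperative draw is less firm elsewhere. Section 2.4.1 says: "This will be recorded preoperatively, if possible, and at both follow-up intervals". In Table 2.4.1 the row "Blood Sample to Lab" carries the conditional code before surgery and the mandatory code at 3-6 months and 1 year.

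Section 2.4.10 promises descriptive statistics for every hemolytic measure taken, and then: "These will be compared by t-test or chi square test as appropriate to PMA results at equivalent time periods". The comparator is the original PMA experience with other valve sizes (section 2.0, Valve effectiveness). The sample is "approximately 20 and at least 15 patients", and section 2.1 ties the US submission to an international standard under which "at least 15 patients will be followed for one year".

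**The concern.** The design yields before-and-after measurements of the same markers, but the plan never links them within a patient. The only named tests compare group values with the PMA at a given time. NYHA class does get a cross-tabulation of changes over time (section 2.0); hemolysis has no counterpart. The laboratory definition of ongoing hemolysis in section 2.4.5 uses fixed limits relative to the normal range, so it does not use the baseline either.

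Two things are at stake. The first is precision: if preoperative and follow-up values are correlated, adjustment removes part of the residual variance, which is useful with so few patients. The second is bias: the comparator is historical and covers other valve sizes, and the trial admits patients of any age, including those having an existing prosthesis replaced. If the groups differ before surgery in a way that persists, an unadjusted follow-up comparison attributes that difference to the valve.

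**Working it through.** The plan has no figure to reproduce. The 15 patients come from an adopted standard, not a power calculation, and the documents give no alpha, effect size, standard deviation, correlation or PMA sample size for these markers. Everything below except n is therefore an assumption.

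**Inputs.** From the documents: n = 15, the minimum. Assumed: PMA group m = 50 or 200; two-sided alpha 0.05; equal standard deviations, set to 1; correlation rho between preoperative and follow-up values of 0.3 to 0.7.

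**Formulas.** For a two-sample t-test with true difference d, the noncentrality is d / sqrt(1/n + 1/m). ANCOVA replaces the standard deviation by sqrt(1 - rho²). Raw change replaces it by sqrt(2(1 - rho)).

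**Residual spread relative to the follow-up level**

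| rho | ANCOVA variance, 1 - rho² | ANCOVA SD | Raw change SD |
|---|---|---|---|
| 0.3 | 0.91 | 0.95 | 1.18 |
| 0.4 | 0.84 | 0.92 | 1.10 |
| 0.5 | 0.75 | 0.87 | 1.00 |
| 0.7 | 0.51 | 0.71 | 0.77 |

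Raw change beats the level only when 2(1 - rho) < 1, that is, rho > 0.5.

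**Power of ANCOVA.** First find the d that gives the unadjusted test 80% or 50% power. For m = 50 these are 0.84 and 0.59 SD; for m = 200 they are 0.75 and 0.53 SD. Then divide d by sqrt(1 - rho²). To the nearest point the results are the same for both values of m:

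| Unadjusted power | rho 0.3 | rho 0.4 | rho 0.5 |
|---|---|---|---|
| 80% | 84% | 86% | 90% |
| 50% | 54% | 57% | 62% |

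The lost degree of freedom changes these by about 0.1 point. The calculation assumes all 15 patients have a baseline and the groups are similar before surgery; missing baselines or imbalance would reduce the gain.

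**Raw change on the same footing.** With m = 200 and a true difference of 0.5 SD, the level has 46% power. Raw change has 35%, 46% and 67% at rho 0.3, 0.5 and 0.7; ANCOVA has 50%, 57% and 74%.

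**Bias, for illustration.** Suppose the groups differ by 0.5 SD before surgery and the valve has no effect. The expected follow-up difference is 0.5 × rho, or 0.15, 0.25 and 0.35 SD at rho 0.3, 0.5 and 0.7. With m = 200 the nominal 5% test then rejects 9%, 15% and 26% of the time; with m = 50, 8%, 13% and 22%. The documents do not show whether such an imbalance exists.

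**Missing baselines.** If 40% of 15 patients lack a preoperative sample, 15 × 0.6 = 9 pairs remain. The within-patient change detectable with 80% power at rho 0.7 then rises from 0.60 to 0.83 SD.

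**The case against.** The strongest objection is that the follow-up level is the more direct measure of hemolysis on the study valve. Hemolysis from a failing prosthesis should end when that prosthesis is removed, and the exclusion criteria keep out patients with another prosthetic valve left in place. The change score is what mixes removal of the old valve with the effect of the new one: a patient could improve on the old state while the new valve still damages blood. This stands. A reader might infer that within-patient change settles the hemolysis question without the PMA, and it does not. Change can only be supportive.

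A reader might also infer that section 2.4.10 tests postoperative levels alone. It does not say so. It covers all hemolytic measures at equivalent time periods, so a preoperative comparison with the PMA fits its wording. That comparison could reveal a group imbalance, but would neither adjust for it nor use the pairing.

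Nor is the baseline assured. Section 2.4.7 reads as routine, while section 2.4.1 and Table 2.4.1 make the draw conditional, so the number of pairs is unknown.

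Finally, ANCOVA against the PMA needs patient-level preoperative values from that source. The protocol refers only to clinical results presented in the PMA and does not show that such values exist. If they do not, none of the power gain above is available. The plan also admits that small numbers limit power and commits to assessing it. These points limit the size of the concern, but no section fills the gap.

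**Conclusion.** The concern holds in limited form. Section 2.4.10 specifies unadjusted comparisons with the PMA and no baseline-adjusted or within-patient analysis of the hemolysis panel, although the protocol calls for the measurements that such an analysis needs, the preoperative one only where possible.

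For ANCOVA, and not for raw change, the gain is about 4 to 10 points of power from a starting point of 80%, or 4 to 12 from 50%, for rho between 0.3 and 0.5. It rests on assumed correlations and PMA sizes and on the availability of patient-level PMA baselines. Any bias removed cannot be sized from the documents. The planned comparison is not invalid; this is a worthwhile but minor addition.

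**What to change.** Add to section 2.4.10:

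> Where patient-level preoperative values exist in the PMA data, the 3-6 month and 1-year comparisons of continuous hemolysis markers will also be made by ANCOVA with the preoperative value as covariate, on the log scale for skewed markers. The unadjusted comparison of all patients will still be shown. Within-patient change from the preoperative value to each late visit will be reported with a 95% confidence interval as a supportive summary, stating the number of pairs and noting that change also reflects removal of the diseased valve.

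Sections 2.4.1 and 2.4.7 and Table 2.4.1 should also be reconciled on the status of the preoperative sample, so that the expected number of pairs is clear.

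The cost is analysis wording and a few tables, with no new procedure. Patients without a preoperative sample drop out of the adjusted and change analyses, and ANCOVA uses one degree of freedom. The unadjusted comparison is kept, so nothing now planned is lost.
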